5.2.4 Data analysis

Table 4: Analysis plan

Research questions	Data sources	Analysis
Objective 1 – To determine the prevalence of respectful care during institutional delivery in Gombe state	Household survey	 Descriptive statistics to profile the study sample in numbers & percentages Descriptive statistics to determine the frequency of reported cases of respectful care from household interviews Descriptive statistics to determine the frequency of reported case of respectful care across socio-demographics Appropriate regression models will be used to explore the relationship between respectful care indicators and demographic characteristics. Potential confounders will be accounted for in all regression models
Objective 2 – To validate self-report of respectful maternity care	Observation of birth (gold standard) Exit interviews Follow-up interviews	 Descriptive statistics to characterize the study sample in numbers & percentages Descriptive statistics to determine the frequency of observed cases of respectful care from direct observation of births, exit and follow-up interviews Descriptive statistics to determine the frequency of reported case of respectful care across socio-demographics

- Sensitivity and specificity
- McNemar's test

Table 5: Socio-demographic characteristics & potential cofounders

Potential confounders	Measures
Age in years	Mean/ SD
Education level	Primary or less/ Secondary or more
Religion	Christianity/ Islam/ Other/ None
Ethnic group	Fulfulde/ Hausa/ Igbo/ Yoruba/ Others
Marital status	Never married/ Married/ Divorced/Separated/ Widowed
Employment status	Employed/ Unemployed
Wealth quintile	Lowest/Second/ Middle/ Fourth/ Highest
Number of previous births	Mean/ SD
Antenatal care visits for the/ index pregnancy	Mean/ SD
Time of delivery	Day/ Night
Days of the week (for observation of births)	Monday/ Tuesday/ Wednesday/ Thursday/ Friday/ Saturday/ Sunday

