1.2 Overview of this study

The IDEAS project is part of this wide partnership with GSPHCDA, Pact, SFH, C4C and E4A working on MNH in Gombe, as a measurement, learning and evaluation (MLE) grant. IDEAS project aims to improve the health and survival of mothers and babies through generating evidence to inform policy and practice. In line with IDEAS project's overarching aim, the study described here will generate empirical evidence on the quality of MNH care as it relates to the frequency and nature of RMC during institutional delivery in Gombe state, to inform state-level and global actions to better promote RMC, and to improve measurement methods for RMC. The study will aim to answer the following the research questions:

Q 1 What is the prevalence of respectful maternity care during institutional delivery in Gombe State? (Objective 1)

To be determined in two ways: 1) prevalence of respectful maternity care based on how frequently mothers regarded the interaction with health workers or health facility conditions

during their last institutional delivery to be respectful, through household surveys of mothers with births in the 24 months prior to interview; 2) prevalence of RMC based on how frequently the interactions with health workers or facility conditions during institutional delivery are deem (by general consensus) to be humiliating or undignified, through observation of births (in line with submission by Freedman et al¹¹).

Q 2 What is the validity of self-reported measures of respectful maternity care?

To be determined by comparing observable respectful maternity care behaviors documented during observation of births as gold standard measures of RMC, compared to reported occurrence of RMC during exit interview with observed women on discharge from facility and again during household-follow interview with observed women 6-12 months after birth to test the validity of self-reporting i.e. do women report their experience of RMC consistently, and extent of normalization of RMC i.e. the extent to which some aspect of RMC are normalized in Gombe.

Q 3 What utilities do women attach to dimensions of respectful maternity care during institutional delivery in Gombe State?

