5.2.2 Exit interviews with observed women

Sample – each woman whose birth was observed (target recruitment of 320 women) is invited to interview as she leaves the facility. Women are asked a set of questions about the clinical and respectful care they received during labour and childbirth. Data collectors will be well trained to maximise reliability of assessment.

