5.2.3 Household follow-up with observed women

Sample – each woman whose birth was observed and was interviewed after discharge before exit will be asked for her consent for a follow-up interview at home six months later. At follow-up, women will be asked the same set of questions and same choice experiment as in the exit interview. Data from the choice experiment at follow-up will be compared with data on choice experiment from the exit interview to assess the stability of derived utilities from time-1(t0-month) and time-2 (t6-months). Data collectors will be well trained to maximise reliability of assessment.

Sample size for validity testing of exit interview and household follow-up interview responses compared to the gold standard observations. To analyse the agreement between observed and reported RMC behaviours we will calculate sensitivity and specificity of reported to observed. This statistical approach does not test a specific hypothesis, but focuses on the width of the confidence intervals around agreement when interpreting results: the larger the number of follow-up interviews we are able to achieve the more narrow the confidence intervals will be.

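### The listed Objective 2 analyses cannot show whether women give the same answers at exit and at follow-up, which Q2 asks

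*Protocol*

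**What the plan says.** Protocol section 1.2 (Q2) compares the observed birth, as gold standard, with the woman's report at exit and again at a home interview 6 to 12 months after birth. It gives the purpose as "to test the validity of self-reporting i.e. do women report their experience of RMC consistently". Section 5.2.3 has the exit questions asked again at follow-up, so each indicator yields a pair of answers per woman. Section 5.2.2 sets a "target recruitment of 320 women".

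On analysis, section 5.2.3 states: "To analyse the agreement between observed and reported RMC behaviours we will calculate sensitivity and specificity of reported to observed". It continues: "This statistical approach does not test a specific hypothesis, but focuses on the width of the confidence intervals around agreement when interpreting results". Table 4 in section 5.2.4 lists for Objective 2 descriptive statistics on observed and reported frequencies, "Sensitivity and specificity" and "McNemar's test". It does not say which pair of sources McNemar's test compares or how its result bears on validity. No statistic is named for agreement between the two interviews.

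**The concern.** Consistency between two interviews is a property of each woman's pair of answers. Sensitivity and specificity need a reference standard, and neither interview is one for the other. The only other inferential analysis listed is McNemar's test. Its null hypothesis is that the two discordant cells are equal, that is, that the proportion answering yes is the same in both sources. Women who change their answers in opposite directions cancel out in that comparison.

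The part of Q2 about consistent reporting over 6 to 12 months could therefore go unanswered, or be answered from a statistic that cannot see the inconsistency. This bears on Objective 2 and on the stated aim of improving measurement methods for respectful care.

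**Working it through.** The protocol gives no power, significance level or precision figure for this analysis, so there is no stated figure to reproduce.

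**Inputs.** 320 pairs (section 5.2.2). Prevalence of 23%, the lowest indicator in Table 3 (desired privacy), with 50% for comparison. Assumed, because the protocol gives no values: two-sided 5% level, independent pairs, and the accuracy and switching rates below.

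**Step 1. Do sensitivity and specificity fix exit/follow-up agreement?** Let both interviews have sensitivity and specificity 0.80, so 20% of women are wrong at each interview. The planned sensitivity and specificity are identical in all three cases:

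- The same women err both times: agreement 100%.
- Errors independent: agreement 0.8² + 0.2² = 0.68.
- Different women err each time: agreement 1 − 0.2 − 0.2 = 0.60.

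For kappa at 23% prevalence, the reported proportion is 0.23 × 0.80 + 0.77 × 0.20 = 0.338, and chance agreement is 0.338² + 0.662² = 0.552.

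- Independent errors: (0.68 − 0.552)/(1 − 0.552) = 0.28 (unrounded inputs).
- Different women: (0.60 − 0.552)/(1 − 0.552) = 0.11.

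At 50% prevalence chance agreement is 0.50, and the two values are 0.36 and 0.20.

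**Step 2. Does McNemar's test separate these cases?** In the second and third cases the discordant answers split evenly (16% each way and 20% each way), so the null is true and the test rejects about 5% of the time. In the first case there are no discordant pairs to test.

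**Step 3. Direct switching between interviews.** Let 30% of women change their answer, half each way. The expected discordant cells are 320 × 0.15 = 48 and 48. The chi-square version without continuity correction rejects in about 5% of studies and the exact version in about 4%. With 200 pairs (assumed loss to follow-up) the rates are again about 5% and 4%. Percent agreement is 70%.

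- Kappa at 50% prevalence: (0.70 − 0.50)/0.50 = 0.40.
- Kappa at 23% prevalence: chance agreement is 0.23² + 0.77² = 0.646, so (0.70 − 0.646)/(1 − 0.646) = 0.15.

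**Step 4. Would the missing statistic be informative at this size?** For 70% agreement, the 95% half-width is 1.96 × √(0.70 × 0.30/320) = 0.050, or 5 points. With 200 pairs it is 6.4 points. Clustering of births within the ten facilities could widen both.

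**Step 5. Report against observation.** For a true value of 0.90 at 320 women, the half-width is 1.96 × √(0.09/74) = 6.9 points for sensitivity (74 observed positives at 23% prevalence) and 1.96 × √(0.09/246) = 3.7 points for specificity (246 negatives). If reports were unrelated to observation but had the same total, sensitivity would be p and specificity 1 − p, which sum to 1. The planned analysis shows that failure directly.

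**The case against.** The strongest reply is that section 5.2.3 already names the agreement analysis, sensitivity and specificity read through confidence intervals, and applies it to both interviews against observation. McNemar's test is then only a supplement. It suits the paired frequencies that Table 4 describes, and it suits the normalization part of Q2 in so far as normalization pushes reports in one direction. All of this stands.

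A reader might infer more: that McNemar's test is the plan's criterion for validity, so that useless indicators would pass and accurate ones fail. The documents do not support that. No section reads a McNemar p-value as valid or invalid. Nor is rejection under accurate reporting a false alarm. With sensitivity and specificity of 95% at 23% prevalence, the expected discordant cells at 320 pairs are 3.7 and 12.3, and the test rejects in 60% of studies (exact version 51%). But reported prevalence is then 0.23 × 0.95 + 0.77 × 0.05 = 25.7%, a real over-report of 2.7 points. Near 50% prevalence with equal error rates, rejection is close to 5%.

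A reader might also see a contradiction between Table 4 listing a test and section 5.2.3 stating "This statistical approach does not test a specific hypothesis, but focuses on the width of the confidence intervals around agreement". That sentence describes sensitivity and specificity, and it does not rule out a supplementary test.

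Two further replies carry some weight. Consistency in Q2 could mean only consistency with observation; on that narrow reading the gap closes. And the choice of coefficient is commonly left to an SAP, which is not at hand. But Q2 glosses validity as consistent reporting and the same questions are repeated at follow-up, so comparing the two interviews is the natural reading. The point is also not which coefficient is used: Table 4 sets out the Objective 2 analyses, and those it lists cannot answer the question.

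**Conclusion.** The point holds for exit against follow-up only. Identical sensitivity and specificity (80% each, assumed) are compatible with exit/follow-up agreement anywhere from 60% to 100%. McNemar's test stays at about 5% rejection when 30% of women switch evenly (assumed), whether there are 320 pairs or 200. It misses inconsistency only where switching roughly balances; one-directional change would show. For report against observation the planned analysis is adequate. The conclusion does not depend on the particular rates chosen, because it follows from what each statistic measures; the rates only show how large the gap can be. It is worth correcting, but it does not undermine Objective 2 as a whole.

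**What to change.** In Table 4, under Objective 2:

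1. Add, for exit against follow-up and for each indicator, the percentage of women giving the same answer and a chance-corrected coefficient such as kappa, each with a 95% CI.
2. Keep sensitivity and specificity with confidence intervals as the basis for validity against observation.
3. Keep McNemar's test, or the paired difference in prevalence with its 95% CI. State which sources it compares, label it as net reporting bias only, and say that a non-significant result is not evidence of agreement or validity.

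The cost is a wording change and a few more lines of analysis on tables the study will already have. No extra participants or data are needed. Reported consistency may look less favourable than the totals alone would suggest.

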5.3 Choice experiment

The study design for objective 3 (to determine the utilities associated with different dimensions of RMC) is described here.

5.3.1 In-depth interviews

To have a deeper understanding of mother's experience of RMC in their recent birth an in-depth interview will be conducted first. Due to the sensitive nature around the topic of disrespect and abuse, a more relaxed atmosphere in which to collect detailed information on thoughts, behaviours and experiences in-depth is required. As stated above, women with recent births will be recruited and interviewed, the person that accompanied them to the health facility will also be recruited and interviewed to capture comprehensive information on both the mothers experience of RMC and what was observed by the person that accompanied them.

Potential participants will be recruited by the researcher in collaboration with the community leaders. Study participants will be recruited from two LGAs: LGA with the lowest facility birth (Kwami LGA), and LGA with the highest facility birth (Kaltungo LGA), based on IDEAS household survey August 2016. For the in-depth interviews, from the 2 LGAs 25 women with recent facility birth (0-6 months or later, but not more than 12 moths since last birth) will be interviewed, if possible the person that accompanied them as well. 25–30 participants are the minimum sample size required to reach saturation and redundancy in grounded theory studies that use in-depth interviews.²

The interviews will be conducted in the women's homes (or a place of their choosing) by the researcher (NU), to be assisted by a trained female research assistant who will take notes and record

² Shari L. Dworkin (2012). Sample Size Policy for Qualitative Studies Using In-Depth Interviews. Arch Sex Behav (2012) 41:1319–1320

the interviews. In instances where the husband or household head does not agree to having a male interviewer or the mother herself is not comfortable with a male interviewer, the trained female research assistant will conduct the interview and capture the interview on audio recorder. The interview will focus on general problems faced by pregnant women, their motivations for giving birth in health facility and for selecting a health facility, their attitudes towards health facility deliveries, their perception on quality and satisfaction with interaction with the provider. Standard IDI procedures will be followed, an interviewed guide will be used to ensure that all relevant issues are covered. The interviews will be conducted in July 2017. Data collection will take the form of field notes, supported by recordings. Interview sessions will be recorded using audio capturing devices, with the permission of the participants and saved in a password locked computer. At the end of each data collection session, the sound recordings, field notes and consent forms, will be stored securely. Recording will be transcribed, and the data analysed using content analysis.

5.3.2 Focus group discussions

The in-depth interview will be followed by focus group discussions to gain insights into the women's shared understandings of RMC during facility delivery and the ways in which individuals are influenced by others in a group situation. The FGDs will be used to explore women experiences from their recent facility-based birth including their interaction with health workers and condition of place of delivery to review or validate the attributes derived from the in-depth interviews. Four FDGs will be conducted, two FDGs in each the LGA: with low facility birth (Kwami LGA) and two FGDs in LGA with high facility births (Kaltungo LGA), with mothers with recent births 0-6 months or later, but not more than 12 moths since last birth - 3 to 4 four FGDs are considered sufficient to answer simple research questions³. Twenty-four participants will be recruited, 6 per focus group – for optimal result, 6-12 participants per focus group has been recommended⁴. To account for possible drop-out, 5 additional participants will be recruited as stand by, as recommended by Krueger RA⁵. Participants for the FGDs will be recruited by the researcher in collaboration with the community leaders from the communities around the health facilities. Standard FGD procedures will be followed, due to the sensitive nature of RMC, a trained female will moderate the sessions, supported by the researcher (NU) who will take notes and record the sessions. The objectives of the FGDs will be to have group consensus around themes on reasons for giving birth in health facility, perception of quality of care received and interaction with health care providers. Further, mother's opinions and perceptions on manifestations and indicators of disrespectful care during facility birth will be explored, dimensions of RMC identified in literature and document review and in-depth interviews will be used as a guide.

_

³ Krueger RA & Casey MA (2000) Focus Groups: A Practical Guide for Applied Research, 3rd ed. Thousand Oaks, CA: Sage Publications.

⁴ Krueger RA & Casey MA (2000) Focus Groups: A Practical Guide for Applied Research, 3rd ed. Thousand Oaks, CA: Sage Publications.

⁵ Krueger RA (1994) Focus Groups: A Practical Guide for Applied Research. Thousand Oaks, CA: Sage Publications.

The FGDs will be conducted in July 2017, after the in-depth interviews. Data collection will take the form of field notes, and audio recordings. Interview sessions will be recorded using audio capturing devices, with the permission of the participants and saved in a password locked computer. At the end of each data collection session, the sound recordings, field notes and consent forms, will be stored securely. Data analysis will be carried out using content analysis.

5.3.3 Choice experiment – conjoint analysis

"Preferences" are an economic concept that refers to the values individuals attach to options from which they must make choices. In health care, patients or clients often have strong preferences associated with treatment or service options. A survey based on conjoint analysis (also called "choice experiments") will be used to measure women preferences for dimensions of RMC. Conjoint analysis is theoretically grounded within the field of economics and routinely used in consumer research. More recently, the method has been applied in health economics and public health research to measure preferences for health care delivery and treatment options. ¹⁷

For the conjoint analysis, identified dimensions of RMC will be decomposed into their general attributes (e.g. physical abuse, verbal abuse, stigma & discrimination etc.) and attribute levels (e.g. attribute levels for physical abuse: beaten, slapped, kicked, or pinched during delivery etc.). Then, scenarios that reflect RMC during facility birth will be created by randomly choosing among attribute levels. When the survey is administered, the respondent will be presented with pairs of RMC scenarios. From each pair, the respondent will be asked to choose the scenario they prefer. Based on the choices made, the path-worth utilities for RMC attributes can be derived. Further, important potential covariates (e.g. age, gender, etc.) will be included to facilitate aggregation of utilities for different subgroups.

Sawtooth software (www.sawtoothsoftware.com), part of the SSI Web software platform, will be used to design the choice-based conjoint-analysis survey. Using the choice-based conjoint module, a fixed set of profiles can be created that draws from a subset of the full-choice design. The software's module could sample from a subset of the full-choice design for each respondent while ensuring level balance and near-orthogonality within each respondent's profile. With this approach, systematic correlations among interactions common in fixed designs can be avoided, allowing for both main effects and higher-order interactions to be robustly estimated especially with good sample sizes. Additionally, by using a unique randomized design for each respondent context effects are reduced. However, with

- 14 -

6.

⁶ Johnson R, Orme B. Getting the most from CBC. Sequim: Sawtooth Software Research Paper Series, Sawtooth Software; 2003.

this design heterogeneity could be confounded in case of taste heterogeneity and scale differences.¹ Table 3 describe the steps involved.

Table 6. Steps and activities involved

Steps	Activities
Identifying attributes	Identify dimensions or attributes of RMC through qualitative research involving (1) review of published and grey literature and (2) focus group discussion with the target population to augment the secondary data. Example of attributes of RMC includes physical abuse, non-consented care, non-confidential care, non-dignified care.
Assigning attribute levels	Use information generated from qualitative methods above to assign attribute levels. Attribute levels will reflect the range of RMC situations that mothers are likely to experience, e.g. attribute levels for non-dignified care: harsh tone; harsh language; unkind expression. To aid cognition each attribute will have not more than three levels.
Generating the choice sets	Use conjoint Sawthooth software to generate attribute level combination to create hypothetical scenarios — create choice sets. To obtain orthogonal and balance design fractional factorial design will be used.
Pre-testing the questionnaire and data collection	Pre-test, evaluate the process and revise the survey. Use trained fieldworkers to administer the questionnaire to respondents.
Analysing of DCE data	Generate individual level estimates of the part-worth of each mother's utility function. Determine the value associated with each dimension of RMC. Perform segmentation/sub-group analysis based on mother's sociodemographic characteristics.

Sample – the choice experiment will be administered during home follow-up interviews: during follow-up at home in November December 2017 to the same post-partum women with live birth that were observed during childbirth and interview at exit in July 2017.

Sample size – For the choice-based experiment, suggestion of sample size determination by Johnson and Orme will be used, which suggests that the sample size required for the main effects depends on the number of choice tasks (t), the number of alternatives (a), and the largest number of levels for any of the attributes (c) according to the following equation: N>500c/(t×a),⁷ if t =15 (i.e. 15 choice tasks) and a =2 (i.e. # of alternatives) and c =6 (i.e. largest # of levels), then the required sample size =500x6 \div 15x2 =100.

